3. OBJECTIVES AND ENDPOINTS

Table 3: Objectives and Endpoints

Objectives	Endpoints
Primary	

 To evaluate immune responses elicited by [REDACTED]-μg dose of licensed Spikevax or Investigational mRNA-1273.815 against the XBB.1.5 strain 	
 GM value of nAb against XBB.1.5 at Day 15
Secondary	

 To evaluate the safety of the [REDACTED]-μg licensed Spikevax or Investigational mRNA-1273.815 	
 SAEs, AESIs, and AEs leading to withdrawal from the study on Day 1 through 15 days after injection

 To evaluate immune responses elicited by [REDACTED]-μg dose of licensed Spikevax or Investigational mRNA-1273.815 against the XBB.1.5 strain 	
 SRR of nAb against the XBB.1.5 strain at Day 15, where seroresponse is defined as nAb value change from baseline (preinjection Day 1) below the LLOQ to $\geq 4 \times$ LLOQ, or at least a 4-fold rise if baseline is \geq LLOQ GMR of nAb against the XBB.1.5 at Day 15 between the 2 treatment groups

Abbreviations: AE = adverse event; AESI = adverse event of special interest; GM = geometric mean; GMR = geometric mean ratio; LLOQ = lower limit of quantification; mRNA = messenger ribonucleic acid; nAb = neutralizing antibody; SAE = serious adverse event; SRR = seroresponse rate.

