1.3. Schedule of Activities

Table 2: Schedule of Activities

Visit Number	Screening ¹	V1	V2 (EoS)	UNS ²
Type of Visit	C	C	C	C
Study Visit Day	D0 ¹	D1 ¹	D15	N/A
Window Allowance (Days)	-7	0	±3	N/A
Days Since Injection	N/A	0	14	N/A
Informed consent form	X			
Randomization, study injection (including 30-minute post-injection observation period)		X		
Confirm participant meets inclusion and exclusion criteria	X			
Physical examination including vital signs ³	X	X	X	X
Pregnancy testing		X		
Blood for SARS-CoV-2 serology (antinucleocapsid antibody) ⁴		X		
Blood for immune response to vaccination ⁵		X	X	
Nasal swab sample for SARS-CoV-2 ⁴		X	X	
Recording of SAEs, AESIs, AEs leading to withdrawal and concomitant medications relevant to or for the treatment of the SAEs, AESIs, and AEs leading to withdrawal ⁶		X	X	X
Recording of concomitant medications and nonstudy vaccinations ⁷		X	X	X
Study completion			X	

Abbreviations: AE = adverse event; AESI = adverse event of special interest; C = clinic visit; D = day; EoS = end-of-study; ICF = informed consent form; IMP = investigational medicinal product; M = month; RT-PCR = reverse transcriptase polymerase chain reaction; SAE = serious adverse event; SARS-CoV-2 = severe acute respiratory syndrome coronavirus 2; UNS = unscheduled visit; V = visit.

¹. The Screening Visit and Day 1 (study injection) Visit can be combined and occur on the same day. Collection of SAEs, AESIs, and AEs leading to withdrawal will begin after signing of ICF.

2. A participant can also be seen for an unscheduled visit at any time during the study. An unscheduled visit may be prompted by new or ongoing AEs. The study site also has the discretion to make safety telephone calls or send text messages to remind the participant about visits, or follow-up on ongoing or outstanding issues.

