2.3.1. Risk Assessment

As with all injectable vaccines, immediate systemic allergic reactions to vaccination, ranging from mild (eg, urticaria) to severe (eg, anaphylaxis) can occur. These reactions are very rare and are estimated to occur once per 450,000 vaccinations for vaccines that do not contain allergens such as gelatin or egg protein ([Zent et al 2002](#)). As a precaution, all participants will remain under observation at the study site for at least 30 minutes after injection.

Vasovagal syncope (fainting) can occur before or after any vaccination, is usually triggered by the pain or anxiety caused by the injection and is not related to the substance injected. Therefore, it is important that standard precautions and procedures be followed to avoid injury from fainting.

As with other IM injections, the study vaccines should be given with caution in individuals receiving anticoagulant therapy or those with thrombocytopenia or any coagulation disorder (such as hemophilia) because bleeding or bruising may occur following an IM administration in these individuals.

Local ARs are expected after IM injection. These are typically mild, transient, and self-limited and may include pain, erythema (redness), or swelling/induration (hardness) at the injection site and/or ipsilateral underarm swelling/tenderness.

Systemic ARs may also occur after study intervention administration, the majority of which are of mild to moderate in severity. Systemic ARs reported with mRNA-1273 vaccines may include fatigue, headache, myalgia, fever, chills, arthralgia, vomiting and/or nausea.

There have been very rare (<1 in 10,000 recipients) reports of myocarditis and pericarditis ([Section 10.4](#)) occurring after injection with COVID-19 mRNA vaccines. The majority of the cases have been reported in adolescent and young males, within 7 to 14 days after the second or subsequent injections. These are typically mild cases, and individuals tend to recover within a short time following conservative treatment. Healthcare professionals and study participants should be alert to the signs and symptoms of myocarditis and pericarditis ([Gargano et al 2021](#)).

Safety Considerations for Unencapsulated RNA:

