8.3.2. Time Period and Frequency for Collecting of Safety Information

All SAEs will be collected from the signing of the ICF until EoS at the timepoints specified in the SoA ([Section 1.3](#)). All SAEs will be recorded and reported to the Sponsor or designee immediately and under no circumstance should this exceed 24 hours, as indicated in [Section 8.3.7](#). The Investigator will submit any updated SAE data to the Sponsor within 24 hours of it being available.

All AEs leading to discontinuation will be collected from the signing of the ICF until the EoS at the timepoints specified in the SoA ([Section 1.3](#)).

All AESIs will be collected from the signing of the ICF until EoS at the timepoints specified in the SoA ([Section 1.3](#)).

Investigators are not obligated to actively seek information on AEs or SAEs after conclusion of the study participation. However, if the Investigator learns of any SAE, including a death, at any time after a participant has been discharged from the study, and the Investigator considers the event to be reasonably related to the study intervention or study participation, the Investigator must promptly notify the Sponsor.

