3.2.1. Safety Endpoint

- SAEs, AESIs, and AEs leading to withdrawal from the study on Day 1 through 15 days after injection.

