Baseline value, unless specified otherwise, is defined as the most recent non- missing measurement (scheduled or unscheduled) collected before the dose of IMP. For immunogenicity tests, the baseline is defined as the most recent non- missing measurement (scheduled or unscheduled) collected before or on the dose date of IMP.

Age: unless otherwise specified, age is calculated as the age at screening.

Study day relative to the injection will be calculated as below:

- a) study day prior to the injection will be calculated as: date of assessment/event – date of the injection;
- b) study day on or after the date of the injection will be calculated as: date of assessment/event – date of the injection + 1;

If untreated, the randomization date will be used as reference date for study day.

Unscheduled visit measurements will be included in analysis as follows:

- In scheduled visit windows per specified visit windowing rules
- In the derivation of baseline
- In individual participant data listings as appropriate

The analysis visit windows for protocol-defined visits are provided in [Appendix 2](#).

Incomplete/missing Data:

- Imputation rules for missing or partial missing dates of prior/concomitant medications and procedures are provided in [Appendix 4](#).
- Imputation rules for missing or partial missing AE dates are provided in [Appendix 5](#).
- If the immunogenicity results are reported as below the LLOQ (eg, < 0.1), the numeric values will be replaced by $0.5 \times \text{LLOQ}$ in the summary. If the immunogenicity results are reported as greater than the upper limit of quantification (ULOQ) (eg, > 3000), the

numeric values will be replaced by ULOQ in the summary if the numeric values are not available (i.e., if numerical values are available, the numerical values are used).

Other incomplete/missing data including immunogenicity will not be imputed, unless otherwise specified.

Treatment Groups

The following vaccination groups will be used for summary purposes:

- μg Investigational mRNA-1273.815
- μg licensed Spikevax
- Overall (optional)

All analyses and data summaries/displays will be provided by vaccination group using appropriate analysis population, unless otherwise specified.

Baseline SARS-CoV-2 status is determined by using virologic and serologic evidence of SARS-CoV-2 infection on or before Day 1.

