6.4.1. Unsolicited Adverse Events

An AE is defined as any untoward medical occurrence associated with the use of a drug in humans whether it is considered drug related or not. SAEs, AESIs (defined in Protocol Table 4), and AEs leading to discontinuation of study participation will be collected throughout the study. All AEs started after the injection will be reported in summary tables.

Unsolicited AEs will be coded by SOC and PT according to MedDRA dictionary.

All summary tables for unsolicited AEs will be presented by SOC and PT for AEs with counts of participants included. Given study duration is approximately 2 weeks, the unsolicited AEs will be summarized throughout the study.

When summarizing the number and percentage of participants with an event, participants with multiple occurrences of the same AE or a continuing AE within SOC or PT group will be counted once. Separate listings for corresponding AE tables will also be provided.

In addition, adverse events based on CDC wording cased definition of pericarditis, myocarditis, and myopericarditis occurring after receipt of study vaccines (defined in Protocol Appendix 4) will be listed if data is available.

The number of events and number of participants with occurrences of selected AEs of clinical interests identified by SMQ throughout the study will be summarized for narrow scope, narrow and broad scope, separately.

6.4.1.1.AEs by System Organ Class and Preferred Term

The following summary tables of AEs throughout the study will be provided by MedDRA SOC and PT using frequency counts and percentages:

- All unsolicited AEs leading to discontinuation from participation in the study,
- All unsolicited AESIs.

6.4.1.2.Serious Adverse Events

The summary table of serious AEs throughout the study will be provided by SOC and PT using frequency counts and percentages.

Death events will be provided in a separate listing.

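### Does the secondary safety endpoint promise 15 days of follow-up that the visit schedule does not deliver?

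*Protocol*

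**What the plan says.** The endpoint in Protocol Section 3 (and Table 1 of the synopsis) is "SAEs, AESIs, and AEs leading to withdrawal from the study on Day 1 through 15 days after injection". SAP 3.2.1 uses the same period: "AEs leading to withdrawal from the study on Day 1 through 15 days after injection".

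The Schedule of Activities in Protocol 1.3 makes Visit 2 (Day 15) the end-of-study visit. Its timing rows read "Days Since Injection N/A 0 14 N/A" and "Window Allowance (Days) -7 0 ±3 N/A". The study-day rule in SAP 6.1 fits this: "study day on or after the date of the injection will be calculated as: date of assessment/event – date of the injection + 1".

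On collection, Protocol 8.3.2 says "All AESIs will be collected from the signing of the ICF until EoS at the timepoints specified in the SoA" and treats SAEs and AEs leading to discontinuation the same way. Protocol 8.2 lists SAEs and AESIs as monitored from the Day 1 vaccination to end of study. On analysis, SAP 6.4.1 notes that the study lasts about two weeks and says "the unsolicited AEs will be summarized throughout the study".

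**The concern.** The endpoint, read literally, ends at study Day 16, while the last scheduled contact is on Day 15. A participant seen exactly on target leaves one day before the stated period ends, and one seen at the early edge of the window leaves four days before. A late visitor can contribute an event 16 or 17 days after injection that lies outside the endpoint but is tabulated under SAP 6.4.1. So the stated and analysed periods can differ in either direction.

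Two things would be at stake. First, a zero count might be read as resting on 15 days of observation when most participants had 14 or fewer. Second, the protocol's risk section places most reported myocarditis and pericarditis cases "within 7 to 14 days after the second or subsequent injections", and a visit on Day 12, 13 or 14 ends observation inside that range.

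**Working it through.** **Inputs.** Target visit Day 15 and window ±3 (Protocol 1.3); study day = days since injection + 1 (SAP 6.1); endpoint limit of 15 days after injection (Protocol Section 3, SAP 3.2.1); about 200 participants (Protocol 1.1); cardiac reports in fewer than 1 in 10,000 recipients (Protocol 2.3.1).

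**Step 1: reproduce the schedule's figure.** Days since injection = study day − 1 = 15 − 1 = 14, which is the figure in the Schedule of Activities.

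**Step 2: apply the window.**

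| Study day of visit | Days after injection | Difference from 15 |
|---|---|---|
| 12 | 11 | −4 |
| 13 | 12 | −3 |
| 14 | 13 | −2 |
| 15 (target) | 14 | −1 |
| 16 | 15 | 0 |
| 17 | 16 | +1 |
| 18 | 17 | +2 |

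Four of the seven permitted days fall short of 15 days and three reach it. These are calendar days, not participants. They say nothing about how many people are affected unless visits are spread evenly over the window, which the documents do not state. The wider Day 12 to 22 window in SAP Appendix 2 applies to immunogenicity and vital signs, not to adverse events.

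**Step 3: separate the slip from the window.** At target the shortfall is 15 − 14 = 1 day, or 1/15 = 6.7% of the stated period. Day 1 to Day 15 inclusive is 15 − 1 + 1 = 15 calendar days, which is probably where the 15 came from. The rest of the 11-to-17 spread is the ordinary effect of a ±3-day visit window. It would remain under any fixed-day wording: with Day 15 as the limit, the earliest permitted visit would still be 14 − 11 = 3 days short.

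**Step 4: follow the period through to the tables.**

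- Collection: to the end-of-study visit (Protocol 8.2 and 8.3.2).
- Protocol analysis: Protocol 9.4.2 gives no cut-off day for the safety summaries.
- SAP analysis: 6.4.1 tabulates everything starting after injection, over the whole study.
- Observation time: SAP 6.2.1 summarizes time from injection to completion or discontinuation in the Safety Set. Under SAP 6.1 such summaries are by treatment group, with mean, SD, median, minimum and maximum.

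The 15-day limit is not used to select events at any step. Replacing it with a limit that matches collection would leave each of these steps as it is.

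**Step 5: size of the cardiac argument.** Expected cases over the whole risk period, both arms together: 200 × 1/10,000 = 0.02, and the protocol's rate is an upper figure, so fewer than 0.02. If the true rate were ten times higher, the figure would be 0.2. Only the part falling in the last one to three days of the 7-to-14-day range could be missed, and an on-target visit covers all 14 days.

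**The case for a change.** The strongest case for a change is that this endpoint is all the safety evidence the trial defines. Solicited reactions are not collected (Protocol 8.3.1.5), no safety laboratory tests are scheduled (8.2.5), and there is no clinical experience with lots at the reduced encapsulation limit (2.3.2). Counts may well be zero, and a zero can be read only with its true observation time. Nothing after the last visit fully closes the gap: investigators need not look for later events, and the duty to report those they learn of covers related SAEs, not non-serious AESIs. The same 15-day phrase recurs for concomitant medications in Protocol 6.9.2, while the Schedule of Activities records them to the end-of-study visit. An inconsistency that costs a few words to remove might as well be removed.

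What stands is the inconsistency itself and the point that a zero needs its observation time. The second is already met by the duration summary in SAP 6.2.1, whose minimum and median would show early departures. A further row counting participants observed for at least 14 days would be a presentational preference. The risk of over-reporting does not stand, because no planned table claims 15 days and SAP 6.4.1 itself describes the study as about two weeks. Nor is a late visitor's event on day 16 or 17 a distortion: it adds safety information and hides nothing.

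**Conclusion.** The endpoint wording is one day longer than the target follow-up (15 against 14 days), and permitted visits give 11 to 17 days. This is a clerical slip between two ways of counting days. Collection and analysis agree with each other, the trial has no hypothesis test (Protocol 9.2), and aligning the wording would alter no data, table or conclusion, so no change to the plan is called for. Protocol Tables 1 and 3, Protocol 6.9.2 and SAP 3.2.1 do need to be read consistently with the Schedule of Activities. Analysts following SAP 6.4.1 will do so without further instruction.

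This rests on two assumptions: that the safety tables are produced over the whole study as SAP 6.4.1 states, with no undocumented cut at 15 days, and that the study report describes follow-up from the planned duration summary rather than from the endpoint line. The cardiac figure also assumes that the protocol's rate of fewer than 1 in 10,000 applies to these adults. The protocol says most reports came from adolescent and young males.

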4. STUDY DESIGN

4.1. Overall Design

The study is a Phase 3b, randomized, observer-blind, active-controlled, clinical study to assess the immunogenicity of an Investigational mRNA-1273.815 COVID-19 vaccine in previously vaccinated adults. Randomization will be stratified by age (18 to <65 years, and \geq 65 years).

The study comprises 3 scheduled in-clinic visits including a Screening Visit (Screening and dosing can be performed on the same day) per [Section 1.2](#) and [Section 1.3](#). This study will be conducted in compliance with the protocol, GCP, and all applicable regulatory requirements.

In this multisite study, participants will be randomized to either licensed Spikevax or Investigational mRNA-1273.815 with a wider RNA encapsulation lower-limit specification. The percent RNA encapsulation lower-limit of the Investigational mRNA-1273.815 vaccine is no more than **CCI** lower than that of the licensed Spikevax vaccine, both of which target the Omicron subvariant XBB.1.5. The Investigator, study staff, study participants, study site monitors, and Sponsor personnel (or its designees) will be blinded to the IMP administered on Day 1 until study end.

With SARS-CoV-2 expected to be circulating in the general population during the study, blood samples will be tested at baseline (preinjection Day 1) for the development of Ab directed against nonvaccine antigen (eg, Ab against the nucleocapsid protein), which will signify infection with SARS-CoV-2.

To assess the vaccine-induced immune responses, blood samples will also be collected from all participants on Day 1 (preinjection) and Day 15 for measurement of SARS-CoV-2 specific nAb responses.

In addition, participants will have nasal swab samples collected before the injection on Day 1 as well as on Day 15.

To monitor for safety, safety data will be collected and will include SAEs, and AESIs, and AEs leading to discontinuation from study participation.

4.2. Scientific Rationale for Study Design

This is a descriptive Phase 3b study designed as a randomized, observer-blind, active-controlled, clinical study to assess the immunogenicity of Investigational mRNA-1273.815 vaccine compared to the licensed Spikevax vaccine, both containing the updated XBB.1.5 strain, in previously vaccinated adults.

This study is being conducted to generate clinical data to support widening the percent RNA encapsulation lower-limit specification. Data generated from the study may also contribute to knowledge and understanding of the mRNA LNP and its effect on vaccine-elicited immunogenicity.

4.3. Justification for Dose

The **CCI**- μ g dose level of the Investigational mRNA-1273.815 is the same as the current dose for licensed Spikevax.

The percent RNA encapsulation lower-limit of the Investigational mRNA-1273.815 vaccine is no more than CCI lower than that of the licensed Spikevax vaccine, both of which target the Omicron subvariant XBB.1.5.

Nonclinical data demonstrate comparable immunogenicity (nAb GMTs) of mRNA-1273 over a range of percent RNA encapsulation CCI (Section 2.2). Mouse immunogenicity has also been shown to be consistent with human immune responses to mRNA-1273 vaccines (Chalkias et al 2022b; Chalkias et al 2023a; Scheaffer et al 2023; Wu et al 2021). Accordingly, it is anticipated that Investigational mRNA-1273.815 vaccine will have similar immunogenicity as licensed Spikevax.

4.4. End-of-Study Definition

The EoS is defined as the date when last data are available.

A participant is considered to have completed the study if the participant has completed all periods of the study including the last visit or the last scheduled procedure shown in the SoA (Section 1.3).

5. STUDY POPULATION

Prospective approval of protocol deviations to recruitment and enrollment criteria, also known as protocol waivers or exemptions, is not permitted.

5.1. Inclusion Criteria

Participants are eligible to be included in the study only if all of the following criteria apply:

1. Male or female, at least 18 years of age at the time of consent (Screening Visit) who previously received:
 - a. At least 2 COVID-19 vaccines as primary series (mRNA or non-mRNA or a combination of both) AND
 - b. At least 1 mRNA booster dose (third dose).
2. Capable of giving signed informed consent which includes compliance with the requirements and restrictions listed in the ICF and in the protocol.
3. Participant has provided written and signed informed consent for participation in this study, including all evaluations and procedures as specified in this protocol.
4. Investigator's assessment that participant understands and is willing and physically able to comply with protocol-mandated follow-up, including all procedures.
5. PNCBP may be enrolled in the study. Nonchildbearing potential is defined as surgically sterile (history of bilateral tubal ligation, bilateral oophorectomy, hysterectomy) or postmenopausal (defined as amenorrhea for ≥ 12 consecutive months prior to Screening [Day 0] without an alternative medical cause). A FSH level may be measured at the discretion of the Investigator to confirm postmenopausal status.
6. POCBP may be enrolled in the study if the participant fulfills all of the following criteria:
 - a. Has a negative pregnancy test on the day of injection prior to vaccine dose being administered (Day 1).
 - b. Has practiced adequate contraception or has abstained from all activities that could result in pregnancy for at least 28 days prior to Day 1.
 - c. Has agreed to continue using an effective contraception through 2 weeks following injection.

Note: a list of acceptable contraceptive methods is listed in [Section 10.3](#).

- d. Is not currently breastfeeding.

Adequate female contraception is defined as consistent and correct use of a contraceptive method approved by US FDA ([Section 10.3](#)) or local health agency in accordance with the product label.

